2.3. Exploratory Objectives

The exploratory objectives of the study are:

- To describe and photograph clinical phenotypes of moderate-to-severe AD in skin of color participants, ≥ 12 years old and associated dupilumab treatment responses
- To assess erythema and pigmentation changes related to moderate-to-severe AD in skin of color participants ≥ 12 years old through clinical assessments, patient-reported severity and impact, and direct colorimetric measurement in AD lesional, hyperpigmentation lesional, and non-lesional skin
- To assess skin dryness changes in moderate-to-severe AD in skin of color participants, ≥ 12 years old through clinical assessment of dryness and patient-reported severity and impact
- To assess pre and post dupilumab structural changes in skin of color AD lesional, hyperpigmentation lesional, and non-lesional skin via Optical Coherence Tomography (OCT) with possible additional non-invasive imaging at the discretion of the investigator (including line field confocal OCT and/or reflectance confocal microscopy)
- To study dupilumab mechanism of action (related to efficacy and/or safety), the biology of IL-4R, IL-4, IL-13, and related pathways, AD, and related diseases.

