3.2. Rationale

3.2.1. Rationale for Study Design

The primary purpose of this study is to provide additional data on the use of dupilumab in adolescent and adult skin of color participants ≥ 12 years old with moderate-to-severe AD. Existing data on the use of dupilumab in self-reported racial and ethnic subgroups comprising skin of color support efficacy and safety profiles that are consistent with overall studied AD populations, though sample sizes with dosing per USPI are limited in minority subgroups (Alexis, 2019). Epidemiologic data suggest that AD may be more prevalent, persistent, and severe in skin of color participants even when controlling for geographic and socioeconomic factors (Brunner, 2019) (Kim, 2019). Moreover, AD presents with distinct clinical manifestations in the skin of color population that may contribute to diagnostic uncertainty and complicate assessment of disease activity and severity (Kaufman, 2018b). Information regarding unique clinical features and mechanisms of disease progression specifically characterizing skin of color AD as well as dupilumab treatment responses have not yet been prospectively collected and will support advancements of AD management in this subpopulation with disproportionate disease burden and evidence for undertreatment.

This study was designed with a 24-week treatment duration because this period of time is considered sufficient to assess near maximal extended treatment effects across AD phenotypes in adolescent and adult skin of color participants treated with dupilumab. Additionally, this period of treatment is sufficiently long to observe participants after appropriate steady-state drug concentrations are achieved. Based on pharmacokinetic (PK) simulations, in the absence of a loading dose, the time to steady-state is expected to be 12 weeks for a 200 or 300 mg Q2W regimen, and the use of a loading dose in this study will reduce the time to steady-state for the Q2W regimen, as has been observed previously. Our intent is to continue to observe participants for a period of approximately 16 weeks beyond attaining steady-state drug concentrations. This will ensure capture of treatment effects on subtypes of AD that more commonly appear in skin of color that are reported to be more treatment refractory (ie, nummular AD). Additionally, an extended treatment period is required to describe changes in pigmentation and xerosis related to AD improvement but known to lag in time course.

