4.1.3. Exploratory Endpoints

The exploratory endpoints are:

- Proportion of participants with each category of AD phenotypes, including morphological features, at each visit through week 24
 - Localized AD
 - Flexural AD
 - Extensor AD
 - Nummular AD
 - AD with prurigo nodules
 - Follicular AD
 - Papular AD
 - Lichenoid AD
 - Psoriasiform AD
- Change from baseline in post-inflammatory hyperpigmentation severity scale (PHSS) at each visit through week 24

- Change from baseline in patient-reported Dyspigmentation NRS at each visit through week 24
- Change from baseline in patient-reported Xerosis NRS at each visit through week 24
- Change from baseline in SCORAD dryness component at each visit through week 24
- Photography substudy at selected sites; 2D/3D/dermoscopic, at AD lesional, hyperpigmentation lesional, and non-lesional sites, baseline, week 16, and end of treatment
- Colorimetry substudy at selected sites: change from baseline in erythema index and change from baseline in melanin index at AD lesional, non-lesional, and hyperpigmentation lesional skin, at each visit through week 24
- OCT substudy with possible additional non-invasive in vivo imaging including line field confocal OCT and/or reflectance confocal microscopy at a single study site; non-invasive in vivo imaging performed at AD lesional, hyperpigmentation lesional, and non-lesional sites at baseline, week 4, week 16, and week 24

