DLQI, CDLQI	
• Mean and change from baseline in Dermatology Life Quality Index (DLQI; age ≥ 16) at each visit through week 24• Percent change from baseline in Dermatology Life Quality Index (DLQI; age ≥ 16) at each visit through week 24• Percent of patients with ≥ 4-point decrease from baseline in DLQI at each visit through week 24• Mean and change from baseline in Children’s Dermatology Life Quality Index (CDLQI; age < 16) at each visit through

	
week 24
 
• Percent change from baseline in Children's Dermatology Life Quality Index (CDLQI; age <16) at each visit through week 24• Percent of patients with ≥ 4-point decrease from baseline in CDLQI at each visit through week 24
HADS	
• Mean and change from baseline in Hospital Anxiety and Depression Scale (HADS) total score, anxiety and depression sub-scores at each visit through week 24• Mean and change from baseline in Hospital Anxiety and Depression Scale (HADS) anxiety and depression sub-scores at each visit through week 24• Percent change from baseline in Hospital Anxiety and Depression Scale (HADS) total score, anxiety and depression sub-scores at each visit through week 24• Percent change from baseline in Hospital Anxiety and Depression Scale (HADS) anxiety and depression sub-scores at each visit through week 24• Percent of patients with Anxiety score < 11 among patients with baseline Anxiety score ≥ 11 at each visit through week 24• Percent of patients with Depression score < 11 among patients with baseline Depression score ≥ 11 at each visit through week 24
AD phenotypic description	
• Percent of each phenotype at baseline• Percent of phenotypes reported as dominant at baseline• For each dominant phenotype, anatomic distribution of lesions at baseline

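### SAP 5.7.2 limits the AD phenotype analysis to baseline although the protocol endpoint runs by visit to week 24, and no planned analysis relates phenotype to response

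*SAP*

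**What the plan says.** **Protocol**
- Section 4.1.3 lists as an exploratory endpoint "Proportion of participants with each category of AD phenotypes, including morphological features, at each visit through week 24", and names nine categories. Table 1 schedules the assessment at baseline and at weeks 2, 4, 8, 12, 16, 20 and 24, plus any early termination visit. Section 9.2.2.2.5 records one dominant morphology and marks the others as present or absent.
- The first exploratory objective in Section 2.3 is "To describe and photograph clinical phenotypes of moderate-to-severe AD in skin of color participants, ≥ 12 years old and associated dupilumab treatment responses".
- Section 3.2.1 gives several reasons for 24 weeks. Two concern phenotype: "this period of time is considered sufficient to assess near maximal extended treatment effects across AD phenotypes", and, on continued observation, "This will ensure capture of treatment effects on subtypes of AD that more commonly appear in skin of color", with nummular AD as the example of a more refractory subtype. Others do not: the intent to "continue to observe participants for a period of approximately 16 weeks beyond attaining steady-state drug concentrations", and the statement that "an extended treatment period is required to describe changes in pigmentation and xerosis related to AD improvement".

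**SAP**
- Section 4.4.2 places AD phenotypic description among the secondary efficacy data.
- The method table in Section 5.7.2 has three phenotype items: "Percent of each phenotype at baseline"; the share of phenotypes recorded as dominant, at baseline; and the anatomic distribution of lesions for each dominant phenotype, at baseline.
- Section 5.8.4, under physical examination, plans a summary by phenotype and dominance and names no visit.
- The subgroup list in Section 5.7 has seven factors: AD duration, weight, BMI, age, sex, race and Fitzpatrick type.
- Section 5.7 also promises by-visit graphs for efficacy variables in general, and Section 6.3 sets by-visit conventions for all efficacy data and physical examination.

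**The concern.** Nearly every other row of the 5.7.2 table is specified by visit through week 24, so the baseline wording in the phenotype row looks deliberate. A programmer who follows that row produces baseline tables only, and a stated protocol endpoint is not reported.

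The second gap concerns the objective. It asks for phenotypes together with their treatment responses, and nothing in the SAP crosses the two. Any later table of response by phenotype would be chosen after the data are seen, across nine categories. The topic is central to this population: both the protocol introduction and SAP 1.1 describe follicular, lichenoid and papular forms as reported more often in black patients, and both say that rigorous prospective characterization of presentation and response is lacking.

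**Working it through.** **Step 1. Endpoint against the 5.7.2 method row.**
- Phenotypes (Protocol 4.1.3): 9. Scheduled visits with phenotype (Table 1): baseline plus 7 post-baseline visits = 8.
- Proportions in the endpoint table: 9 × 8 = 72.
- Named in SAP 5.7.2: 9 × 1 = 9, which is 9/72 = 12.5%. Not named there: 9 × 7 = 63.

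**Step 2. Does other SAP text supply the 63?**
- 5.8.4 gives percent by phenotype and dominance but no time point. It could be read either way.
- 6.3 maps records to visits and does not itself create tables. Its list includes vital signs, which the SAP marks as not applicable in 4.5.4 and 5.8.3, so appearing in that list does not establish a planned table.
- The by-visit graph sentence in 5.7 is general, and the specific 5.7.2 row points the other way.

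The SAP is therefore unclear about post-baseline proportions. It is not certain that they are omitted.

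**Step 3. Phenotype against response.** Subgroup factors in 5.7: 7, none of them phenotype. Analyses specified in the SAP that cross phenotype with EASI-75 or any other outcome: 0. The texts in Step 2, even read generously, concern proportions over time and not response.

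**Step 4. What a response-by-phenotype table could show.** The plan's own figure first: 120 × (1 − 0.15) = 102, against about 105 in Protocol 11.2. The figure of 105 corresponds to 1 − 105/120 = 12.5% dropout. The gap of 3 is small, and the plan's wording (up to 15%, approximately) allows for it. I use 102 as the number with a week 24 EASI, which assumes that missing week 24 data equal dropout.

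The documents give neither phenotype prevalence nor an expected response rate. I assume prevalence of 5% to 50% and EASI-75 response of 50% to 70%. With n = 102 × prevalence and x = n × response, both rounded to whole participants, the exact (Clopper-Pearson) 95% limits are:
- lower = 2.5% quantile of Beta(x, n − x + 1)
- upper = 97.5% quantile of Beta(x + 1, n − x)

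| Assumed prevalence | n | At 50%: x, 95% interval | Half-width (points) | At 70%: x, 95% interval | Half-width (points) |
|---|---|---|---|---|---|
| 5% | 5 | 2, 5.3% to 85.3% | 40.0 | 4, 28.4% to 99.5% | 35.6 |
| 10% | 10 | 5, 18.7% to 81.3% | 31.3 | 7, 34.8% to 93.3% | 29.3 |
| 20% | 20 | 10, 27.2% to 72.8% | 22.8 | 14, 45.7% to 88.1% | 21.2 |
| 30% | 31 | 16, 33.1% to 69.8% | 18.4 | 22, 52.0% to 85.8% | 16.9 |
| 50% | 51 | 26, 36.6% to 65.2% | 14.3 | 36, 56.2% to 82.5% | 13.2 |
| All | 102 | 51, 39.9% to 60.1% | 10.1 | 71, 59.7% to 78.3% | 9.3 |

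Dominant phenotype puts each participant in one category, so the average category would hold 102/9 ≈ 11 participants, close to the 10% row. The table is feasible and descriptive, and imprecise for rare forms.

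**The case against.** The strongest reply is that the SAP does more than 5.7.2 shows. It has a second phenotype summary not limited to baseline (5.8.4), and general rules that efficacy data are shown by visit (5.7, 6.3). This stands in part. A reader might infer that seven of the eight scheduled assessments certainly go unanalysed; the documents do not support that, only that the specific row and the other text disagree.

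A reader might also infer that the reason for 24 weeks of treatment is left unanswered. That is not supported either. Refractory subtypes are one of several reasons in Protocol 3.2.1, and the SAP analyses pigmentation and xerosis through week 24 (PHSS, Dyspigmentation NRS, Xerosis NRS, SCORAD dryness). Section 3.2.1 justifies a duration; it does not promise results by phenotype.

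The two gaps also differ in standing. By-visit proportions are a protocol endpoint. Response by phenotype is not: it rests on an exploratory objective, and Protocol 11.4.3.1 leaves the detail of subgroup analyses to the SAP. Part of that objective is photographic, and SAP 5.7.3 leaves the photography methods to vendor documents that are not available here. This makes the response table the weaker request, but it does not supply a planned analysis.

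Finally, it would go too far to say that the trial cannot answer the phenotype questions. Phenotype and EASI are collected at the same visits, and the SAP allows revision. What is missing is prespecification; no data are lost.

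**Conclusion.** The point holds in two parts.

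1. **By-visit proportions.** The only phenotype analysis with a stated time point covers 9 of the 72 proportions in the protocol endpoint. The undated summary in 5.8.4 and the general by-visit conventions leave the other 63 unclear. This is a mismatch with a stated endpoint and should be corrected.
2. **Response by phenotype.** None is planned, although the first exploratory objective asks for treatment responses. A descriptive table would serve that objective at little cost.

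The endpoint is exploratory in the protocol, the study tests no hypothesis, and the primary EASI-75 result does not change. The counts come directly from the documents. The interval widths rest on the assumed prevalence and response rates and on 102 participants with week 24 data.

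**What to change.** - **SAP 5.7.2:** tabulate each phenotype and the dominant phenotype at every scheduled visit through week 24, and add a baseline-to-week-24 shift table for dominant phenotype. State the denominator for each.
- **SAP 5.8.4:** align it with 5.7.2 by naming the same visits, or replace it with a cross-reference.
- **SAP 5.7:** add a descriptive summary of week 24 EASI-75 by baseline dominant phenotype, with n and an exact 95% interval for each category. State in advance a minimum count below which a category is shown as counts or pooled, and which categories may be pooled. The nine categories mix distribution (such as flexural or extensor) with morphology (such as follicular or lichenoid), so careless pooling could merge the forms of most interest; showing counts avoids this.

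The cost is a SAP revision and a few tables from data already collected. The drawback is wide intervals for rare phenotypes, with half-widths of about 29 to 40 points at n = 5 to 10 under the assumptions above, so the table should be labelled descriptive and not used to rank phenotypes.

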5.7.3. Analyses of Other Efficacy Endpoints

The analyses of other efficacy endpoints (binary and continuous variables) will be conducted in a similar fashion as the primary analysis or secondary analysis. Imaging data and analysis will be provided by vendors.

Assessment	Analysis Method

3D Photography (select sites)	QuantifiCare will provide the methods in additional documents
Colorimetry measurement (select sites)	
Lesional Target Area
 
• Percent change from baseline to week 24 in Melanin Index• Percentage change from baseline to week 24 in Erythema Index 
Non-Lesional Target Area
 
• Percentage change from baseline to week 24 in Melanin Index• Percentage change from baseline to week 24 in Erythema Index 
Hyperpigmented Target Area
 
• Percent change from baseline to week 24 in Melanin Index• Percent change from baseline to week 24 in Erythema Index
Optical Coherence Tomography and non-invasive in vivo imaging (single site)	Vendor will provide the methods in additional documents

5.8. Analysis of Safety Data

The summary of safety will be performed for all patients in SAF.

5.8.1. Analysis of Adverse Events

Summaries of all TEAEs will include:

- TEAEs by primary system organ class (SOC) and preferred term (PT)
- TEAEs by Primary SOC, PT, and Maximum Severity
- Treatment-related TEAEs by Primary SOC and PT
- TEAEs Leading to Death by Primary SOC and PT

- TE-SAEs by Primary SOC and PT
- TEAEs Leading to Study intervention Discontinuation by Primary SOC and PT
- TEAEs by SOC/HLT/PT (incidence with PT $\geq 2\%$)
- AESIs by Primary SOC and PT

Listing TEAEs, serious TEAEs, severe TEAEs, TEASs leading to death and study drug discontinuation will be generated.

5.8.2. Analysis of Clinical Laboratory Measurements

Listing of pregnancy test will be provided.

5.8.3. Analysis of Vital Signs

N/A

5.8.4. Analysis of Physical Exam

Summary of AD Phenotypic Description by percent of patients in each AD Phenotypes and dominance.

5.8.5. Analysis of Biomarker Data

Descriptive statistics for the observed values, change from baseline and percent change from baseline values by treatment and visit will be provided for the following biomarker variables:

Total serum

IgE Antigen-specific IgE

All above analyses will be performed on the FAS.

All observed data, regardless of rescue treatment is used or whether data is collected after study drug withdrawal.

6. DATA CONVENTIONS

The following analysis conventions will be used in the statistical analysis.

6.1. Definition of Baseline for Efficacy/Safety Variables

Unless otherwise specified, the baseline assessment for all measurements will be the latest available valid measurement taken prior to the first administration of study drug in the current study. The following rules specify the determination by both date/time information:

1. For the AE, both date and time of the measurement will be used to determine baseline by comparing with the first injection date and time.
2. For other data except AE, only date of the measurement will be used to determine baseline by comparing with the first injection date if date is available. If no first injection date record available, baseline visit data without available date will be used. If there is no baseline visit, screening visit data without available date will be used.

6.2. Data Handling Convention for Missing Data

Missing data will not be imputed in listings. This section includes the methods for missing data imputation for some summary analyses, if necessary.

Adverse event

If the intensity of a TEAE is missing, it will be classified as “severe” in the frequency tables by intensity of TEAE. For example, if the assessment of relationship of a TEAE to the investigational product is missing, it will be classified as “related” in the frequency tables by relation to the investigational product.

Adverse events start date

AE start date will be used for AE classification. If AE start date is not complete, then the character variable will keep the original incomplete date, the numerical date variable will be imputed and an imputation flag will indicate which date component is missing.

If AE start day is missing, and AE start month and year are not missing: If AE start year is the same as first dose year and the AE start month is the same as the first dose month, then impute AE start day using the day of first dose. If this leads to a date after the AE end date, use AE end date instead. Otherwise impute the AE start day using the first day of the month. If this leads to a date before informed consent, the informed consent date will be used. Imputation flag is ‘D’.

If AE start month is missing, and AE start year is not missing: If AE start year is less than the first dose year, use the informed consent day and month. If AE start year is equal to the first dose year, use the first dose day and month. If this leads to a date after the AE end date, use AE end date instead. If AE start year is after the first dose year, use 01 January. Imputation flag is ‘M’.

If AE start year is missing: Impute AE start date using the day of first dose. If this leads to a date after the AE end date, use AE end date instead. Imputation flag is ‘Y’.

Adverse events end date

The general recommendation is not to impute AE end date.

Medication start and end date missing

To determine whether a medication is pre-treatment medication or concomitant medication or both, the missing medication start date is estimated as early as possible, and the missing medication end date is estimated as late as possible. If the medication start date is missing, the onset day will not be calculated in medication listings.

Prior medication start date

If the start day is missing, and the start month and year are not missing: Impute the start day using the first day of the month. Imputation flag is 'D';

If the start month is missing, and the start year is not missing: Impute the day and month using 01 January. Imputation flag is 'M'.

If start year is missing: Impute start date using 2 years before informed consent date. Imputation flag is 'Y'.

A special note: for start date with year missing, the general principle is not to impute. However in order to simplify the programming flow, the imputation is proposed to in line with the protocol which specifies to collect up to 2 years prior to medication. Since the start date of prior medication will not be used in any analysis, the rule will not impact the analysis result.

Prior medication end date

If end day is missing, and end month and year are not missing: Impute end date using the last day of the month. If this leads to a date on or after first dose intake date, use first dose intake date -1 instead. Imputation flag is 'D'.

If end month is missing, and end year is not missing: Impute end date using 31 December as the day and month. If this leads to a date on or after first dose intake date, use first dose intake date -1 instead. Imputation flag is 'M'

If end year is missing: Impute end date using the first dose intake date -1. Imputation flag is 'Y'.

Concomitant medication start date

The imputation rule for concomitant medication start date is the same as AE start date.

Concomitant medication end date

If end day is missing, and end month and year are not missing: Impute end date using the last day of the month. If this leads to a date after EOS follow-up date, use end of follow-up date instead. Imputation flag is 'D'.

If end month is missing, and end year is not missing: Impute end date using 31 December as the day and month. If this leads to a date after EOS follow-up date, use the end of follow-up date instead. Imputation flag is 'M'.

If end year is missing: Impute date using the end of follow-up date. Imputation flag is 'Y'.

Medication coding

Medications whose ATC level 4 cannot be coded will be summarized by setting ATC4=ATC2 in

the table programs. However, these uncoded ATC level 4 records still need to be confirmed with study DM and study MD.

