5.7.1. Analysis of Primary Efficacy Endpoint (EASI-75)

Primary analyses:

All observed data, regardless of whether rescue treatment is used, or data is collected after study drug withdrawal, will be used to analyze the primary endpoint. Percent of patients achieving EASI-75 at week 24 will be reported. The numerator is the number of patients who achieving EASI-75 at week 24, and the denominator is the number of patients who completed assessment EASI at week 24. Patients with missing data will not be imputed as non-responders. The primary efficacy analyses will be performed on FAS.

Sensitivity analyses:

1. Last observation carried forward – non-responder imputation (LOCF-NRI) approach:

For patients with missing data at week 24 who completed at least 16 weeks of treatment, missing data will be imputed by LOCF from either week 16 or week 20. Patients who received rescue therapy after week 16 will be considered non-responders.

2. Multiple imputation (MI) approach:

Efficacy data through week 24 after rescue medication use will be set to missing first. Missing data will be imputed by MI for 20 times based on patients who have non-missing data. The imputed week 24 EASI will determine EASI-75 response status.

Missing data from the FAS will be imputed 20 times to generate 20 complete data sets by using the SAS procedure MI following the 2 steps below:

Step 1: The monotone missing pattern is induced by Markov Chain Monte Carlo (MCMC) method in SAS procedure MI. The monotone missing pattern means that if a patient has missing value for a variable at a visit, then the values at all subsequent visits for the same variable are all missing for the patient.

Step 2: The missing data at subsequent visits will be imputed using the regression method for the monotone pattern with adjustment for covariates disease severity, and relevant baseline covariates.

The imputation model will include:

- The covariates included the EASI baseline value, the disease severity [IGA 3 vs IGA 4] and measured endpoint values from every clinic visit up to week 24

Week 24 data for each of the 20 complete datasets will be analyzed for EASI-75 response. The SAS MIANALYZE procedure will be used to generate valid statistical inferences by combining results from the 20 analyses using Rubin's formula.

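### SAP 6.2 moves partly dated rescue drugs to an earlier start, so in the LOCF-NRI sensitivity analysis a rescue after week 16 can escape being counted as non-response

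*SAP*

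**What the plan says.** SAP 6.2 first gives a principle for medications: "the missing medication start date is estimated as early as possible, and the missing medication end date is estimated as late as possible". The stated purpose is to sort drugs into pre-treatment, concomitant or both. For concomitant drugs it then says: "The imputation rule for concomitant medication start date is the same as AE start date".

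The AE rule that this imports works as follows:

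- **Day missing:** the first of the month, or the first-dose day if the month and year are those of the first dose.
- **Month missing, same year as first dose:** "If AE start year is equal to the first dose year, use the first dose day and month".
- **Month missing, later year:** "If AE start year is after the first dose year, use 01 January".
- **Year missing:** "Impute AE start date using the day of first dose".

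If the same-month, same-year or missing-year rule gives a date after the recorded end, the end date is used instead.

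SAP 5.4 says that rescue drugs are adjudicated from all recorded medications, so they come from this same record. SAP 5.7.1 uses rescue timing twice. In LOCF-NRI: "Patients who received rescue therapy after week 16 will be considered non-responders". In MI: "Efficacy data through week 24 after rescue medication use will be set to missing first". The primary analysis in the same section uses all observed EASI data whether or not rescue was given.

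**The concern.** Placing an AE early is cautious, because it makes the event treatment-emergent. For a rescue drug the start date does a different job. It decides whether a participant is a non-responder in LOCF-NRI and which EASI values are deleted in MI. No other dating rule exists, so the imputed date from the AE rule is the only one the SAP supplies for this purpose.

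SAP 6.2 itself defends its crude rule for prior-medication start dates on the ground that no analysis uses them. That defence is not available for rescue start dates.

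What is at stake is the value of the sensitivity analyses. Because the primary analysis ignores rescue, these two are the only planned EASI-75 results that take it into account. An error that runs one way in LOCF-NRI weakens the check it is meant to provide.

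**Working it through.** There is no stated figure to reproduce, so the check applies the date rule itself.

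**Inputs.** The rule is from SAP 6.2. Week 16 is target day 113 and week 24 is day 169 (SAP 6.3). I read rescue after week 16 as study days 114 to 169, which is 56 days. The first-dose date is taken as equally likely on each day of a 365-day year (assumption). That gives 365 × 56 = 20,440 combinations.

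**Month missing.** Number the first-dose date *y* = 0 to 364 and the true rescue day *s*.

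- The rescue falls in the first-dose year when *y* ≤ 365 − *s*, and is then dated to day 1. The share is the mean of (366 − *s*)/365. With mean *s* = 141.5 this is 224.5/365 = 61.5%.
- Otherwise it is dated to 01 January, which is study day 366 − *y*. This is at or before day 113 when *y* ≥ 253, that is 112/365 = 30.7%.
- Total moved to week 16 or earlier: 61.5% + 30.7% = 92.2%.

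**Day or year missing.** Full enumeration gives:

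| Missing part | Dated to day 1 | Moved to week 16 or earlier | Mean shift (days earlier) |
|---|---|---|---|
| Day | 0% | 26.4% | 14.8 |
| Month | 61.5% | 92.2% | 112.9 |
| Year | 100% | 100% | 140.5 |

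Across all true rescue days 1 to 169, the imputed date is never later than the true date. In LOCF-NRI the rule can therefore remove a non-responder but never create one.

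**Size in LOCF-NRI.** Shift in points = 100 × *r* × *m* × 0.92 × *q*. Here *r* is the share rescued after week 16, *m* the share of those with the month missing, and *q* the share who would count as responders if not penalised. None of these is in the documents. The assumed ranges are *r* 2 to 15%, *m* 2 to 25%, *q* 30 to 80%.

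- Low: 100 × 0.02 × 0.02 × 0.92 × 0.3 = 0.01 points.
- Middle: 100 × 0.10 × 0.10 × 0.92 × 0.5 = 0.46 points, or 105 × 0.0046 = 0.48 of a participant.
- High: 100 × 0.15 × 0.25 × 0.92 × 0.8 = 2.76 points.

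One reclassified participant is worth 1/120 = 0.83 to 1/105 = 0.95 points, using the protocol 11.2 counts.

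**MI.** A rescue between weeks 16 and 20 that is dated to day 1 loses five valid EASI values (weeks 2, 4, 8, 12 and 16). The participant is then imputed from baseline EASI and IGA severity alone. If only the day is missing, take a shift uniform on 0 to 29 days and visits 28 days apart. The chance of crossing a visit is (0 + 1 + … + 28 + 28)/(28 × 30) = 434/840 = 52%.

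The direction was checked by a large-sample simulation with assumed trajectories and sequential regression imputation. It varied how strongly rescue follows poor response. EASI-75 among the rescued:

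| Link of rescue to poor response | Correct date | Dated to day 1 | Change (points) |
|---|---|---|---|
| Strong | 19.0% | 56.4% | +37 |
| Moderate | 25.6% | 54.0% | +28 |
| Weak | 36.5% | 51.8% | +15 |
| None | 51.8% | 49.7% | −2 |
| Inverse | 65.0% | 50.0% | −15 |

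These changes apply only to misdated participants.

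**The case against.** The strongest reply is that the date rule was written to classify drugs, that rescue is adjudicated separately, and that an unknown month for an on-study rescue should be rare. Protocol 8.3 asks for assessments before rescue is given, at an unscheduled visit if needed. The schedule of events records concomitant drugs at every visit, and CRF data can be queried. The trial is descriptive and its primary analysis does not use rescue timing. All of this stands as a limit on size. It does not remove the point, because the SAP says the rule applies to concomitant start dates and gives no other date for SAP 5.7.1 to use.

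A reader might infer more, and the documents do not support it:

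- **That every missing month becomes the first-dose date.** This holds only when the years match; a later year gives 01 January.
- **That both sensitivity analyses are biased in favour of the drug.** This is established for LOCF-NRI only. In MI it depends on how rescue relates to earlier response. Protocol 8.3 reserves rescue for intolerable symptoms, which makes a favourable direction plausible, not certain.
- **That the prior-medication end-date rule also distorts rescue timing.** For an unknown end year it says "Impute end date using the first dose intake date -1", which sits awkwardly with the late-as-possible principle. Neither sensitivity analysis uses that date, and exclusion criterion 10 (no topical corticosteroid or calcineurin inhibitor within 7 days before baseline) makes an undated carry-over uncommon.
- **That rescue is under-counted.** A rescue dated to the first-dose day is still on treatment, and SAP 5.4 counts participants by drug class after adjudication.

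**Conclusion.** The concern holds in a limited form. Followed as written, SAP 6.2 misdates partly dated rescue drugs early, and in LOCF-NRI that error can only be neutral or favourable. The likely effect there is under about 1 percentage point (0.46 in the middle case; 0.01 to 2.8 over the assumed ranges). In MI it discards valid pre-rescue data, with an uncertain direction.

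This rests on four assumptions: week 16 means day 113; first doses are spread evenly over the year; the LOCF-NRI rescue sentence covers all participants rescued after week 16, not only those with missing week 24 data (a narrower reading shrinks the effect); and partial dates occur at the assumed rates. If no rescue start date is partial, the effect is nil. The primary EASI-75 result does not change in any case. The point is worth fixing because the correction is nearly free and the LOCF-NRI error has nothing to offset it.

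**What to change.** In SAP 6.2, exempt drugs adjudicated as rescue from the AE start-date rule whenever their timing is used in SAP 5.7.1, and state instead:

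1. Query the partial date first.
2. If it stays unresolved, bound the start by the last visit at which the drug was not yet reported, within the known month and year.
3. In LOCF-NRI, count rescue that cannot be placed at or before week 16 as after week 16.
4. In MI, set to missing only EASI values after the bounded date, or report the result under both the earliest and the latest possible date.

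The AE rule can stay for classifying drugs as pre-treatment or concomitant, and the prior-medication end-date rule need not change for this purpose. The cost is one paragraph and a few lines of programming, settled before results are seen. The downside is that a few rescued participants may be counted as non-responders when their true rescue was earlier, which errs on the cautious side.
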